10. DATA AND SPECIMEN BANKING

10.1 Data storage

Patient interview data and provider survey data. Data from patient interviews will be collected in REDCap. The provider survey data via email will be collected in REDCap. Any provider survey filled out by pen and paper will be transferred into REDCap by the project manager.

STU#: 00201638

Upon completion of all study activities, a final de-identified dataset will be created. This dataset will be stored indefinitely on the GIM server for secondary analyses. Only authorized personnel will have access to the dataset.

IVR data. Patients' responses to the questions on the IVR call will be captured in BMC's REDCap. The responses and record ID will be kept in REDCap until the completion of the study and analyses. The identifiable data will be deleted from REDCap within a week. Data for patients whose responses suggest a medication issue are sent to BMC's Mirth system to create the HL7 message that is then sent to the Alliance. Data is stored in Mirth for 7 days before deletion.

10.2 Data description

Interview data noted above will be stored.

10.3 Release of data

Data will not be released.

11. DATA AND SPECIMEN MANAGEMENT

11.1 Data analysis plan

Aim 1 Analysis Plan. The proposed trial uses a cluster-randomized design where the practice location is the unit of randomization. We will randomize 12 locations to two arms (usual care, EMC2) resulting in 6 per arm. Locations will be matched by total number of patients eligible for the study as well as proportion of Spanish speaking patients, with one location from each pair randomized to each arm. We will accrue ~100 patients per location, on average, and conservatively anticipate ≥80% retention at 3-month follow-up. These estimates result in 1200 participants recruited with an anticipated 960 patients (480 per arm, 80 per location) available for primary data analysis.

Medication knowledge associated with high-risk medications is the first primary outcome of interest for Aim 1 (H1), and will be analyzed as a score ranging from 0-100 reflecting the percent of items correct for each medication. Medication use outcomes (proper use, adherence) and detection of ADEs are relevant to the other hypotheses of interest for Aim 1 (H2, H3). Associations between the outcomes and potential confounders at the patient (socio-demographic characteristics, comorbidities, # and type of medications taken, previous history with side effects, literacy, and primary language) and medication (drug type, route of administration) levels will be examined. We intend to use generalized linear mixed models (GLMM) to analyze the data, which can handle data that is missing at random (MAR). Additionally, we will examine rates of missing data, and determine if there are any discernible patterns using GLMMs with a logit link function to predict the presence of missing data. Should we find significant predictors, we will use multiple impute methods and present results as secondary analyses.

To account for the correlated nature of the data from participants at the same practice and multiple observations per patient, we will use GLMMs for analyses of all data, specifying identity link for continuous and the logit link for binary outcomes using PROC GLIMMIX in SAS (v.9.4). Treatment assignment by time will be the independent variable of primary interest and modeled as a fixed effect and practice location as a random effect, with additional subject statement to model correlations within patient. We will also include fixed effects for any potential confounding covariates noted in the descriptive studies. For all GLMM analyses we will report point estimates and 95% confidence

STU#: 00201638

intervals, and the extent to which random effects suggest correlation of outcomes within practice location. Additionally, we will estimate the ICCs for all outcomes to be used in future studies.

Aim 2 Analysis Plan: We will repeat all GLMM analyses described in Aim 1, but with the inclusion of a fixed effect for participants' literacy defined as limited (inadequate or marginal literacy) vs. adequate. We will formally test for differences in intervention effects according to literacy by including a literacy-intervention interaction term. Statistically significant interaction terms ($p < 0.05$) will indicate that the disparities in understanding between the intervention and usual care group vary by literacy level. Similar analyses will be used to test for interactions of intervention effects by age and English proficiency (using Census criteria of 'very well' vs. 'less than very well').

Aim 3 Analysis Plan: Following completion of enrollment, we will determine the extent to which the intervention was implemented as planned in the intervention arm. We will ask patients in the intervention arm if they were counseled, and whether they received the Med Guide Summaries and the post-visit IVR call. Bivariate analyses will be performed to compare relevant outcomes for H4-H7 between arms using t-tests, Wilcoxon Rank-Sum, or χ^2 tests, as appropriate. Aim 3 findings will also directly inform follow-up qualitative investigations in Aim 4.

Aim 4 Analysis Plan: A combination of patient focus groups (N=3; 1 per FQHC site; ~ 6-7 per group) and individual interviews with prescribers and nurses (N=7 per site; 5 prescribers, 2 nurses) will be conducted to understand in detail any barriers to implementation of the EMC2 Strategy. Preliminary findings from Aim 3 highlighting process outcomes and possible 'voltage drops' in implementation will be explored further in Aim 4. In addition, we will contact via phone a convenience sample (n=30) of pharmacies exposed to e-prescribed counseling requests. Feedback will be sought as to whether the order influenced pharmacy behavior. Our conceptual framework will guide discussions and interviews, along with Normalization Process Theory (NPT). NPT follows sociological principles pertaining to the implementation of innovations into practice. It takes the worldview that multifaceted interventions are often needed, and that implementation and integration often depends on: the work (tasks to be completed), who is responsible, how it impacts current practice, and how it is understood by an organization. Suggestions for further improvement of the strategy will be solicited. Discussions will be audio-recorded and transcribed for thematic analyses. Responses will be organized and summarized by provider/patient and component.

Aim 5 Analysis Plan: We will directly measure and assess the provider perspective costs of developing and running the EMC2 Strategy. Specifically, we will estimate the incremental cost of the intervention relative to usual care from the perspective of the Alliance and each FQHC implementing this process and tools. The primary costs of running the EMC2 Strategy involves the limited expenses around printing (printer ink, paper, staff time) as a result of generating new medication information with after-visit summaries. However, we will include estimates for minimal programming maintenance, for both GE Centricity EHR and the IVR system, and will test the sensitivity of results to changes in the maintenance requirements in terms of programmer hours. We also will separately track development costs for software and other programming requirements based on programmer hours. Staff/programmer costs will be measured using tracked time spent on the intervention and wage estimates. We will test the sensitivity of operational costs to different assumptions about the potential use of variable staff using different salaries but assuming the same proficiency in terms of time required. Further, we will assess the sensitivity of estimates to different proficiency levels that could arise from learning by doing.

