3.2 Inclusion and exclusion criteria

Inclusion Criteria (Patients). To be eligible to enroll in the study, patients must attend one of the seven randomized clinics associated with the Alliance-affiliated health center Near North Health Service Corporation. They must also meet all of the following criteria: 1) age 21 and older; 2) English or Spanish speaking; 3) have received a new or changed prescription (i.e. had not been prescribed at Alliance within the previous two years) for one or more of our study medications (Table 1); 4) have a personal phone line (land or mobile).

Inclusion Criteria (Providers). To be eligible to complete the provider survey, providers must see patients at one of the three Near North clinics randomized to the intervention arm (Louise Landau, Komed Holman, Sunnyside).

Study medications. To select these drugs, we reviewed the top prescriptions ordered in 2013 by providers at Alliance FQHCs and selected those that have a Med Guide/REMS requirement. These drugs were reviewed by clinicians and pharmacists to ensure the list was comprehensive and appropriately reflects prescribing behaviors in the clinics. These drugs are diverse by class, indication, duration, side effects, route of administration, and potential for harm. Each has an FDA risk communication goal that presently is not being achieved.

Table 1.

STU#: 00201638

testosterone	escitalopram	sitagliptin and metformin
amiodarone	fluoxetine	exenatide
carbamazepine	paroxetine	liraglutide
divalproex	sertraline	pioglitazone
gabapentin	doxepin	rivaroxaban
lacosamide	imipramine	ciprofloxacin
lamotrigine	mirtazapine	levofloxacin
levetiracetam	colchicine	moxifloxacin
oxcarbazepine	emtricitabine and tenofovir	salmeterol
phenytoin	nevirapine	budesonide and formoterol
pregabalin	fenofibrate	fluticasone and salmeterol
topiramate	clopidogrel	celecoxib
valproic acid	alendronate	diclofenac
aripiprazole	risedronate	indomethacin
quetiapine	pimecrolimus	meloxicam
clonazepam	tacrolimus	sulindac
bupropion	amphetamine	dexlansoprazole
trazodone	methylphenidate	pantoprazole
desvenlafaxine	linagliptin	metoclopramide
duloxetine	saxagliptin	tamoxifen
venlafaxine	saxagliptin and metformin	varenidone
citalopram	sitagliptin	propylthiouracil

alprazolam	ibandronate	mometasone-formoterol
apixaban	lisdexamphetamine	nortriptyline
dexmethylphenidate	lorazepam	olanzapine
diazepam	lurasidone	tramadol
fluticasone-vilanterol		

Table 1 – part 2.

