11.2 Power analysis

The sample size for this study was based on comparisons of the primary outcome of medication knowledge between the two arms (i.e., usual care vs EMC2) at the 3-month interview. We expect

STU#: 00201638

participants in the usual care arm to score an average of 55.6 (SD=28.4) based on a previous study testing comprehension of the FDA standard Med Guides to those to be used in this study. Enrolling 1200 participants and estimating 80% retention at the follow-up interview (n=960, 480 per arm), we will have 80% to detect a minimum difference of 5.5 between the EMC2 and the usual care arm assuming a Type I error of 5%, assuming 100 patients per practice site enrolled at baseline and n=80 available at 3 month follow-up. This effect size was calculated based on an independent t-test with a variance inflation factor to account for the cluster-randomized design. An intra-class correlation coefficient (ICC) of 0.001 was used as we expect the clustering of practice site to have minimal influence on patient outcomes.

Usual care estimates for understanding of risks and demonstrated safe use outcomes were obtained from prior work. For subgroup analyses on these outcomes for Aim 2, we expect roughly 38% to have limited health literacy. Detectable differences at 3 months are based on estimates of 3 patients per provider with limited literacy and 5 with adequate literacy. Detection of ADEs is defined as the number of events recorded in the medical chart out of the total number reported by patients at the 3-month interview. In a study in which 20% of participants reported at least 1 adverse drug event, 35 of their 166 (21%) reported events were recorded in their medical chart. Therefore, the sample size calculation for this outcome was based on 21% of reported ADEs in 20% of our expected sample at 3 months (n=96 per arm, 3 patients per 32 providers, assuming an equal number of providers in each arm will have patients with no ADEs). We will be able to detect a minimum of 18.2 between the EMC2 and the usual care arm. For subgroup analyses by literacy, we assume 1 patient per provider with limited literacy and 2 with adequate literacy.

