19. SETTING

19.1 Research sites.

Sites from which we will recruit participants (via phone) include clinics associated with The Alliance, an EHR user community composed of safety net health centers. The Alliance is an innovator and national leader in using health information technology (HIT) among FQHCs. The Alliance links 67 community health center practices in the metropolitan Chicago area; all are Public Health Service 330-funded FQHCs with federal mandates to care for medically underserved areas. Patients are mostly African American, Latino and low income. Alliance FQHC's share a common EHR (GE Centricity®). Drs. [name] and [name] have a long history collaborating with the Alliance and [name]. We will work specifically with Near North Health Services Corporation, randomizing seven of their clinics.

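### The power statement makes no allowance for the small number of clinics (seven or 12, to be reconciled), and the analysis section names no small-sample method for the arm effect

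*Combined protocol and SAP*

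**What the plan says.** **Clinic count.** Section 19.1 has the sponsor "randomizing seven of their clinics". Section 3.1 also gives seven, and section 3.2 limits the provider survey to "providers must see patients at one of the three Near North clinics randomized to the intervention arm", which leaves four for usual care. Section 11.1 says instead: "We will randomize 12 locations to two arms (usual care, EMC2) resulting in 6 per arm", with locations matched in pairs. Section 29 also refers to 12 locations.

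**Analysis.** Section 11.1 uses mixed models for all outcomes, fitted "using PROC GLIMMIX in SAS (v.9.4". Treatment by time is the term of main interest, "modeled as a fixed effect and practice location as a random effect", with a further term for correlation within patient. Estimates come with 95% confidence intervals. Neither this section nor any other names a degrees-of-freedom method, a small-sample correction, a clinic-level analysis or a permutation test.

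**Power.** Section 11.2 is built on the difference in knowledge score between arms at 3 months: usual-care SD 28.4, 480 analysed per arm, 80 per site, 5% type I error, ICC 0.001, and 80% power for 5.5 points. On method it says: "This effect size was calculated based on an independent t-test with a variance inflation factor".

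**The concern.** When clinics are randomized, the error in the arm effect includes clinic-to-clinic variation, and that is estimated from the clinics rather than the patients. In an unmatched comparison it carries clinics-minus-2 degrees of freedom: 5 with seven clinics, 10 with 12. A variance inflation factor enlarges the standard error but leaves the reference distribution at patient level. The two-sided 5% critical value is 1.960 there, against 2.571 on 5 df and 2.228 on 10.

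Two things are at stake. The stated power may belong to a test that a clinic-randomized trial cannot rely on. And because the analysis section leaves the reference distribution open, the choice could be made after the data are seen, although it changes the interval width by 31% with seven clinics (2.571/1.960 = 1.31) or 14% with 12 (2.228/1.960 = 1.14).

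**Working it through.** **Inputs.** SD 28.4, 480 analysed per arm, ICC 0.001 and 5% type I error (taken as two-sided) are from 11.2. Clinic counts are from 19.1 and 3.2 (seven, as three against four) or 11.1 (12, six per arm). Section 23 recruits equal numbers per arm, so seven clinics means 480/3 = 160 analysed per intervention clinic and 480/4 = 120 per usual-care clinic. With 12 it is 80 per clinic.

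**1. Reproduce the stated 5.5.** Design effect DE = 1 + (m - 1) x ICC, and detectable difference = 2.802 x SD x sqrt(2 x DE/480).
- m = 80: DE = 1.079, SE = 28.4 x sqrt(2.158/480) = 1.904, detectable difference 5.33, power at 5.5 82%.
- m = 100 (enrolled): DE = 1.099, detectable difference 5.38, power at 5.5 82%.
- A patient-level t with 958 df gives 5.34 and 5.39.

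All are within 3% of 5.5. With 10 df, m = 80 gives 5.92. The stated figure therefore matches a normal or patient-level reference, not a clinic-level one.

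**2. Same ICC, clinic-level df.** The multiplier for 80% power from the noncentral t is 3.514 on 5 df and 3.110 on 10 df.
- Seven clinics: SE = 28.4 x sqrt((1.119 + 1.159)/480) = 1.956. Normal reference: 2.802 x 1.956 = 5.48. On 5 df: 3.514 x 1.956 = 6.87, and power at 5.5 is 62%.
- Twelve clinics: SE = 1.904. On 10 df: 3.110 x 1.904 = 5.92, and power at 5.5 is 74%.

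**3. Over a range of ICCs.** Values above 0.001 are assumptions; the documents give none. Each cell is the detectable difference, then power at 5.5.

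| ICC | 7 clinics, 5 df | 12 clinics, 10 df |
|---|---|---|
| 0.001 | 6.87, 62% | 5.92, 74% |
| 0.005 | 8.39, 46% | 6.73, 63% |
| 0.01 | 9.96, 35% | 7.63, 53% |
| 0.02 | 12.52, 24% | 9.16, 39% |
| 0.05 | 18.16, 14% | 12.68, 23% |

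Much of the growth down each column comes from the ICC itself: at 0.005 with seven clinics the normal reference already gives 6.69.

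**4. Type I error for the 3-month arm difference.** 20,000 null trials per ICC, REML random-intercept model, normal data, equal clinic sizes within arm:

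| ICC | 7 clinics, 1.96 | 7 clinics, t on 5 df | 7 clinics, t-test on clinic means | 12 clinics, 1.96 |
|---|---|---|---|---|
| 0.001 | 4.5% | 1.0% | 4.5% | 4.5% |
| 0.005 | 7.0% | 2.1% | 4.7% | 6.1% |
| 0.01 | 8.5% | 3.3% | 4.6% | 6.7% |
| 0.02 | 10.2% | 4.2% | 4.8% | 7.6% |
| 0.05 | 10.6% | 4.8% | 4.8% | 7.8% |

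Separate runs agreed to within about 0.6 of a percentage point. For 12 clinics at ICC 0.005 they ranged from 5.5% to 6.1%.

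**5. Behaviour of the candidate tests at ICC 0.001, seven clinics.** The clinic variance is estimated as exactly zero in 51% of trials. At a true difference of 5.5, the mixed model with fixed 5 df has about 1% type I error and 53-55% power. The t-test on clinic means has about 4.5% error and 60-61% power.

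**The case against.** A reader might infer that the trial's intervals and p-values will be too narrow. The documents do not support that. Section 11.1 is silent on degrees of freedom; it does not choose a large-sample reference, and what the software returns depends on options and coding that are not given. The inflated error rates are a risk conditional on that choice.

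Four further points stand.
- At the plan's own ICC a 1.96 cutoff holds its size, so an analyst who knew the ICC to be 0.001 could use it. But 11.2 offers only an expectation of little clustering, without data, and 11.1 plans to estimate the ICCs. Other sections give reasons for clinics to differ: 11.1 matches them on the share of Spanish speakers, 2.1 names English proficiency and literacy as risk factors for poor understanding, and 9.2 lets each clinic shape its response to flagged concerns.
- Seven clinics cannot be taken as settled, since the analysis section itself says 12. With 12 the effect is milder but remains. If the 12 were analysed as six matched pairs, 5 df would apply again.
- Section 11.1 makes treatment by time the term of interest. If a change contrast is tested, a clinic random intercept largely cancels, and the error rates in step 4 do not apply. The gap would then be the absence of a clinic-by-time variance, which a choice of df alone does not repair. Section 11.2, however, powers the 3-month difference.
- Fixed clinic-level df in the mixed model are very conservative at ICC 0.001, so the remedy has a real cost.

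**Conclusion.** The concern holds in two parts. First, the 80% power for 5.5 points is not supported as written, under either clinic count and even at ICC 0.001, once the arm effect is tested with clinics-minus-2 df: 62% power and a detectable difference of 6.9 with seven clinics, 74% and 5.9 with 12. This rests on an SD of 28.4, 480 analysed per arm, a two-sided 5% test and an unmatched analysis.

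Second, the test of the arm effect is not fully prespecified. If a normal or patient-level reference were used for the 3-month difference, type I error would be nominal at ICC 0.001. It would be about 7% at 0.005, 8.5% at 0.01 and 10-11% at 0.05 with seven clinics, or about 6%, 7% and 7-8% with 12. The documents establish neither that this reference will be used nor that the ICC exceeds 0.001.

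**What to change.** 1. Reconcile the clinic count and the allocation per arm across sections 3.1, 3.2, 11.1, 11.2, 19.1 and 29.
2. Name the 3-month arm difference, the contrast that is powered, as primary. If the change contrast is to be primary, add a clinic-by-time random effect.
3. Prespecify one cluster-level test in 11.1, with the other as sensitivity analysis: either a t-test on clinic means (covariate-adjusted if wanted) with clinics-minus-2 df, or the mixed model with fixed between-clinic df that do not revert to patient level when the clinic variance is estimated as zero. Offering Kenward-Roger or between-clinic df as alternatives would leave the test open, because a data-driven df can become large in the roughly half of trials where that estimate is zero at ICC 0.001.
4. Restate the detectable difference and power in 11.2 with the same df, over a range of ICCs.

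The cost is text and model options, with no change to data collection. Intervals widen by 31% with seven clinics or 14% with 12 relative to a 1.96 reference, and the stated power becomes less favourable. If the ICC really is 0.001 and there are seven clinics, the fixed-df mixed model has about 1% actual error and 53-55% power at 5.5. The clinic-means test loses less, at 60-61%.
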